CORRIDA RCT (2020) (26)	rtCGMS vs isCGMS, 60 T1DM	Time in Hypoglycemia during exercise was lower in rtCGM(6.8% vs 11.4%, p=0.018)& during home phase(5.3% vs 7.3%,p=0.035).

Reddy et al assessed the impact of CGMS and FGM in a high-risk group of people with T1D by a randomized, non-masked parallel group study using a multiple-dose insulin-injection regimen with inclusion of patients with a Gold score of ≥ 4 or recent severe hypoglycaemia. Following 2 weeks of blinded CGM, they were randomly assigned 40

T1D patients to CGM (Dexcom G5) or flash glucose monitoring (Abbott Freestyle Libre) for 8 weeks. The primary outcome was the difference in time spent in hypoglycaemia (below 3.3 mmol/l) from baseline to endpoint with CGM versus flash glucose monitoring. In this trial, 40 participants were randomized to CGM (n = 20) or flash glucose monitoring (n = 20), the participants (24 men, 16 women) had a median (IQR) age of 49.6 (37.5–63.5) years, duration of diabetes of 30.0 (21.0–36.5) years and HbA1c of 56 (48–63) mmol/mol [7.3 (6.5–7.8)%]. The baseline median percentage time < 3.3 mmol/l was 4.5% in the CGM group and 6.7% in the flash glucose monitoring. At the end-point, the percentage time < 3.3 mmol/l was 2.4%, and 6.8% respectively (median between group difference -4.3%, P = 0.006) hence the time spent in hypoglycaemia at all thresholds, and hypoglycaemia fear, were different between groups, favouring CGM. They concluded that CGM more effectively reduces time spent in hypoglycaemia in people with Type 1 diabetes and impaired awareness of hypoglycaemia compared with flash glucose monitoring.

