We are postulating that by application of CGMS for 2 weeks glycemic patterns of individual patients will be identified and the education provided in this regard will change the insight of the individual towards his disease which will culminate in better longer term blood glucose control and already previous studies have shown that glucose readings from the most recent 14 days correlate strongly with 3 months of mean blood glucose, time in ranges, and hyperglycemia metrics (33,34).

Primary objective:

To study the effects of rtCGM vs isCGM on:

- Reduction in HbA1c (at the end of 3 months).

Secondary objectives:

- Reduction in glycemic variability.
- Reduction in hypoglycemic events in adults with Type-1 Diabetes.
- Reduction in Fructosamine (at the end of 2 weeks).
- Quality of life as assessed by QOLID (Nagpal etal) Questionnaire

MATERIALS AND METHODS

1. **Study design:** Open label crossover RCT with 3 arms
2. **Sample size:** Sample size of 17 is requires for a power of 80% to detect 0.5% change in HbA1c between both groups with an alpha of 0.05, Assuming 10% attrition in each group 20 patients will be recruited in all rt-CGMS and is-CGMS and 40 in SMBG arms.
3. **Subjects:** Patients attending Endocrinology OPD at PGIMER Chandigarh
4. **Study Period:** 15th June 2023 to 15th February 2024(last enrolment on 15th August 2023) and last follow up on 15th February 2024.
5. **Study Center:** PGIMER, Chandigarh
6. **Study Population:** Patients who fulfill inclusion and exclusion criteria will be recruited from OPD.

Inclusion criteria :

- Adolescents and adults ≥ 15 years with Type-1 Diabetes mellitus defined by any of the following;
 - Diabetic Ketoacidosis or ketonemia or ketonuria at diagnosis with insulin dependence for survival since diagnosis OR
 - Insulin dependence for survival since diagnosis and any one of the following autoantibody positivity: GAD-65 or IA-2
- Patients on Basal bolus regimen (**Glargine as basal and lispro/Aspart/Glulisine as bolus**);
- Duration of Diabetes > 2 years;

- Insulin dose requirement of at least 0.5U/kg
- HbA1c 8%-12%;
- Gold score<4;
- No previous experience with rt-CGMS and/or is-CGMS;
- Euthyroid status;
- If hypothyroid, then on stable dose of Levothyroxine for last 3 months with normal T4 level;
- Urine albumin creatinine ratio<300 mg/g of Creatinine;
- Those willing to give informed consent prior to enrolment.

EXCLUSION CRITERIA:

- LADA or Secondary Diabetes
- eGFR<60ml/min/1.73 m^2
- Celiac disease;

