- Hb<12g/dl for males and <11g/dl for females;
- Hypoglycemia unawareness defined by Gold score \geq 4;
- HbA1c>12%;
- DKA in previous 3 months;
- Severe Non proliferative Diabetic retinopathy/Proliferative DR/Macular edema;
- Pregnancy;
- Lactation;
- Willing to become pregnant during study;
- Requiring MRI for any existing condition;
- Any chronic illness.

METHODOLOGY

Participants meeting inclusion criteria will be randomized to rt-CGMS, is-CGMS and SMBG arms. Randomization will be done using computer generated random number list. Blocks of patients with HbA1c 8%-10% and 10%-12% will be distributed equally in all 3 groups.

Sample Size: With a 1:1:2 randomization ratio in 3 arms with sample size of 20:20:40 participants in each groups will be required.

Initial training of 2 weeks for all enrolled patients in each of 3 groups about the disease itself, ICR, ISF, carbohydrate counting and bolus dose adjustment based on these parameters will be done, for premeal boluses. **Only those patients will be enrolled who are using Lispro/Aspart/Glulisine for their diabetes control.** All adults enrolled in the rt-CGM group will be placed on rt-CGM Medtronic CGMS for 2 weeks and finger-prick blood glucose will also be monitored by glucometer (SMBG) 3 times on day 1 and then at least 2 times per day with proper record of time. All patients will use same glucometer for SMBG. Physical exercise of at least 30 mins aerobic activity will be required in all patients.

After a week a new Medtronic CGMS will be applied as per the manufacturer recommendation. Those randomized into is-CGM will be placed on Abbott Libre Flash system for 2 weeks. A 3rd group on SMBG will also be there (doing SMBG 4 times a

day- Before breakfast, Before Lunch, and Before Dinner and post meal (after any one meal on rotational basis) and **7 point profile once a week on Sunday**).

During this 2 week intervention phase all the patients will be monitored daily telephonically along with once in a week follow-up visit.

Fructosamine assay will be repeated after 2 weeks in rt-CGMS and is-CGMS groups and glycemic control compared. Thereafter the 3 groups shall use SMBG for monitoring glycemic status as in SMBG group and HbA1c will be repeated at the end of 3 months.

CGMS metrics of the 2 weeks (TBR, TIR ,TAR etc) will be compared in both groups as per ADA recommendations and those with <70% data available will be kept on a new device.

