At the end of 3 months direct cross-over of rt-CGMS group to new is-CGMS group and is-CGMS group to new rt-CGMS group will be done and again fructosamine assay shall

be done at the baseline and at the end of 2 weeks. Thereafter, all the 3 groups shall use same glucometer for SMBG till the end of 6 months where HbA1c will be estimated.

[figure not shown]
Hence, for each participant total 6 months of data will be recorded. Individuals will act as their own control thereby removing confounding factors in analysis

[figure not shown]
be done at the baseline and at the end of 2 weeks. Thereafter, all the 3 groups shall use same glucometer for SMBG till the end of 6 months where HbA1c will be estimated.

[figure not shown]
Hence, for each participant total 6 months of data will be recorded. Individuals will act as their own control thereby removing confounding factors in analysis.

[figure not shown]
All these insulins and CGM systems are a part of routine standard care in management of Type-1 Diabetes Mellitus as endorsed by American Diabetic Association in 2022.

FLOW CHART OF STUDY PROTOCOL

OUTCOME VARIABLES TO BE STUDIED

- Glycemic variability as assessed by CGMS
- Daily average insulin requirement per kg body weight
- Fructosamine assay after 2 weeks in rt-CGMS group and is-CGMS group and HbA1c in each of the 3 groups at end of 3 and 6 months respectively;
- Number of hypoglycemic events especially nocturnal and exercise related events;
- Any complications related to CGM;
- Quality of Life by QOLID (Nagpal et al) Questionnaire.

Statistical Analysis:

Statistical analysis will be performed according to the results obtained from parameters. Discrete categorical data will be represented in the form of either a number or a percentage (%), continuous data, assumed to be normally distributed, will be written as either in the form of its mean and standard deviation or in the form of its median and interquartile range, as per the requirement. The normality of quantitative data will be checked by measures of Kolmogorov-Smirnov tests of normality. ANOVA or Mann Whitney U test will be applied to compare 3 groups at a time depending upon the normality of the data. Proportions will be compared using Chi square or Fisher's exact test, depending on their applicability for 3 groups. All the statistical tests will be two-sided and will be performed at a significance level of $P < 0.05$. Analysis will be conducted using IBM SPSS STATISTICS (version 22.0)

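### Two secondary objectives promise a reduction in glycaemic variability and hypoglycaemic events, but the plan specifies no pre-device value; its CGM data support only a between-device difference

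*Combined protocol and SAP*

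**What the plan says.** All references are to the combined protocol and SAP.

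- **Secondary objectives:** the list includes "Reduction in glycemic variability" and "Reduction in hypoglycemic events in adults with Type-1 Diabetes". Like the primary objective, these compare rt-CGM with is-CGM.
- **Outcome variables:** the first outcome is "Glycemic variability as assessed by CGMS". The hypoglycaemia outcome is "Number of hypoglycemic events especially nocturnal and exercise related events", with no glucose threshold, data source or time window.
- **Inclusion criteria:** "No previous experience with rt-CGMS and/or is-CGMS", so no historic sensor data can serve as a baseline.
- **Methodology, before the device:** "Initial training of 2 weeks for all enrolled patients in each of 3 groups about the disease itself, ICR, ISF, carbohydrate counting" and related skills. No masked sensor, glucose profile or hypoglycaemia count is described for this fortnight.
- **Methodology, on the device:** "CGMS metrics of the 2 weeks (TBR, TIR ,TAR etc) will be compared in both groups as per ADA recommendations". The SMBG arm tests four times a day, with a 7-point profile each Sunday. After the first wear, all three groups follow that schedule.
- **Crossover:** the two CGM arms swap device at 3 months, and patients are meant to serve as their own controls. A baseline is named here for fructosamine, but not for variability or events.
- **Statistical Analysis:** continuous outcomes get ANOVA or Mann-Whitney across three groups. No paired test, mixed model or baseline covariate is listed.

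**The concern.** A reduction needs a starting value. For CGM variability the text provides none: the first sensor reading is taken on the randomised, unmasked device. The SMBG arm has no sensor reading at all, so the planned three-group test cannot be run on this outcome. For hypoglycaemic events, no baseline count is specified.

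Two things are at stake. The report could claim a reduction that its data cannot show. And in a comparison of separate groups on first-period values, an unmeasured starting difference between two arms of 20 could be neither seen nor adjusted for.

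**Working it through.** **The plan's own figure.** The only sample-size figure is for HbA1c: 17 patients to detect 0.5% with 80% power at alpha 0.05, raised to 20 per CGM arm for 10% attrition. No SD is given, so 17 cannot be reproduced, only back-solved. It implies an SD of 0.52 for 17 per arm in parallel groups, or an SD of within-patient differences of 0.74 for 17 pairs. The attrition step gives 17/0.9 = 18.9, or 19, against 20 stated. None of this is disputed here. It supplies n = 20 per arm.

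**Which values exist before a device** (protocol text only)

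| Time | CGM variability | Hypoglycaemic events |
|---|---|---|
| Before entry | none (CGM-naive) | none specified |
| 2 training weeks | none described | none specified |
| First 2-week wear | CGM arms, on device | no source or window given |
| To month 3 | none | glucometer schedule in all arms, but after the first device |
| Second 2-week wear | CGM arms, on device | no source or window given |

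**Size of a hidden starting gap.** The SE of a chance difference in baseline means is SD × √(2/n).

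- n = 20: √(2/20) = 0.316 SD. The 95% range is ±1.96 × 0.316 = ±0.62 SD, and the chance of a gap above 0.5 SD is 11%.
- n = 17: √(2/17) = 0.343 SD. The range is ±0.67 SD and the chance is 14%.

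A share rho of the gap, the correlation between baseline and on-device values, carries into the on-device comparison. The documents give no rho. At an assumed 0.5 this is 0.5 × 0.62 = ±0.31 SD, and at 0.7 it is 0.7 × 0.62 = ±0.43 SD.

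**Error rate.** In 40,000 simulated two-arm trials with 20 per arm and no device effect, the unadjusted test rejected in 5.0% (rho 0.5) and 4.8% (rho 0.7). Only among trials whose hidden gap exceeded 0.5 SD did it reject more often, in 13% and 21%.

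**Precision.** This is the rt-CGM vs is-CGM difference detectable with 80% power, in SD units, with k = 1.960 + 0.842 = 2.802.

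| Analysis | Formula | rho 0.3 | rho 0.5 | rho 0.7 |
|---|---|---|---|---|
| On-device values only, 20 per arm | k√(2/20) | 0.89 | 0.89 | 0.89 |
| Adjusted for a CGM baseline | k√(2(1−rho²)/20) | 0.85 | 0.77 | 0.63 |
| Within patient, 40 crossing over | k√(2(1−rho)/40) | 0.52 | 0.44 | 0.34 |

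In the last row rho is the correlation between a patient's two device periods, and no carry-over or period effect is assumed.

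**Illustration from a cited trial.** In the 40-patient rt-CGM vs flash trial, "The baseline median percentage time < 3.3 mmol/l was 4.5% in the CGM group and 6.7% in the flash glucose monitoring", a gap of 6.7 − 4.5 = 2.2 points. At the end the values were 2.4% and 6.8%, a gap of 4.4. The difference in change is (2.4 − 4.5) − (6.8 − 6.7) = −2.2. Subtracting only rho × 2.2 from 4.4 leaves 3.7, 3.3 or 2.9 points at rho 0.3, 0.5 or 0.7. These are differences of medians, so approximate.

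**The case against.** The strongest reply is the crossover. The objectives compare two devices, and each CGM patient wears both. A stable starting gap cancels in a within-patient contrast, with no pre-device value needed. On the assumptions above, that contrast is also more precise than adding a CGM baseline to a parallel comparison (0.44 against 0.77 SD at rho 0.5). This stands, and it shapes the fix. It does not rescue the wording, for three reasons:

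- Comparing two device periods gives a difference between devices, not a fall from before either.
- The Statistical Analysis lists no within-patient analysis.
- The Hypothesis expects the first wear to change patients' behaviour lastingly, so the glucometer readings before the second device are not untreated values. Nor do they give CGM variability.

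A second reply is that the closest cited trial (60 patients with normal hypoglycaemia awareness) describes no masked run-in and still speaks of reducing hypoglycaemia. That is fair: a masked run-in is not universal among the cited device trials, and the word can loosely mean a lower level on one device than on the other. The plan should say so if that is what it means.

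A reader might also infer that no pre-device value exists for any patient. That goes too far. Glucometer data precede the second device, events are not tied to CGM, and the flow chart could list baseline assessments. For the same reason, the text does not show that the 40 SMBG patients are useless for hypoglycaemia: they test four times a day and are telephoned daily in the intervention phase.

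**Conclusion.** The concern holds in a limited form. On the text as it stands, a reduction from before the device cannot be computed for CGM variability and is not specified for hypoglycaemic events. The CGM data support only a between-device difference in on-device level.

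The cost is lost precision, a starting imbalance that cannot be checked (chance gap about ±0.62 SD with 20 per arm) and an unsupported claim of reduction. Two stronger readings are not supported:

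- **That chance gaps are systematically taken for device effect.** Randomisation keeps overall type I error at 5%, and a gap is as likely to hide an effect as to enlarge it.
- **That this trial would double its apparent effect, as 4.4 against 2.2 points suggests.** Those figures come from a parallel-group trial in patients with impaired awareness or recent severe hypoglycaemia, whereas this trial crosses over and excludes impaired awareness. The factor of two also removes the whole baseline gap; at the assumed rho values it is about 1.2 to 1.5.

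The precision figures rest on assumed correlations, and the within-patient figures also assume no carry-over. These are secondary objectives and the repair is cheap, so the change should be made.

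**What to change.** 1. **Restate and reanalyse.** Word both objectives as the rt-CGM vs is-CGM difference in on-device level over the 2-week wear. Analyse it within patient across the two crossover periods, with device, period and sequence terms, in place of the independent-group tests. Define a hypoglycaemic event, its data source and its window. Make no claim of reduction from a pre-device level based on CGM metrics. This costs wording and an analysis paragraph. Two limits remain: carry-over from the first wear, and sensors that record every 5 and every 15 minutes.

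2. **Add a common baseline, as a supplement.** Collect the existing Sunday 7-point glucometer profile in all three arms on both training Sundays. Report the baseline-adjusted change to month 3, before the crossover, in SMBG variability and in readings below 70 mg/dL. Use month 6 only if the 7-point schedule is confirmed for months 3 to 6, which the text does not restate. The cost is 80 × 2 × 7 = 1,120 strips and a line on the form. The downside is a sparse baseline of 14 readings per patient, taken while training is changing behaviour, that may miss nocturnal events. It supplements the CGM metrics and does not replace them.

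If the flow chart already schedules a baseline recording, bring it into the text and use it in step 2.

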Beck et al conducted a Randomized clinical trial conducted between October 2014 and May 2016 at 24 endocrinology practices in the United States that included 158 adults with type 1 diabetes who were using multiple daily insulin injections and had hemoglobin A1c (HbA1c) levels of 7.5% to 9.9%. Random assignment 2:1 to CGM ($n = 105$) or usual care (control group; $n = 53$) was done in this study and the difference in change in central-laboratory-measured HbA1c level was compared from baseline to 24 weeks. Also, secondary outcome as duration of hypoglycemia at less than 70mg/dL, measured with CGM for 7 days at 12 and 24 weeks was reported. It was found that mean HbA1c reduction from baseline was 1.1% at 12 weeks and 1.0% at 24 weeks in the CGM group and 0.5% and 0.4%, respectively, in the control group (repeated-measures model $P < .001$). At 24 weeks, the adjusted treatment-group difference in mean change in HbA1c level from baseline was $-0.6%$ (95% CI, $-0.8%$ to $-0.3%$; $P < .001$) and median duration of hypoglycemia at less than <70 mg/dL was 43 min/d (IQR, 27-69) in the CGM group vs 80 min/d (IQR, 36-111) in the control group ($P = .002$). Severe hypoglycemia events occurred in 2 participants in each group. This trial

revealed that among adults with type 1 diabetes who used multiple daily insulin injections, the use of CGM compared with usual care resulted in a greater decrease in HbA1c level during 24 weeks.

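### The 80% power claim states no SD, source or test; for the 3-month rt-CGM vs is-CGM comparison it holds only if the SD is about 0.50, which nothing in the protocol supports

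*Combined protocol and SAP*

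**What the plan says.** Materials and Methods, item 2 (Sample size) states: "Sample size of 17 is requires for a power of 80% to detect 0.5% change in HbA1c between both groups", at an alpha of 0.05. It continues: "Assuming 10% attrition in each group 20 patients will be recruited in all rt-CGMS and is-CGMS and 40 in SMBG arms". The Methodology section repeats the 20:20:40 split. Neither place gives an SD, a reference for one, or the test behind the 17.

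The primary objective compares rt-CGM with isCGM on "Reduction in HbA1c (at the end of 3 months"). The Methodology section places the switch at that same point: "At the end of 3 months direct cross-over of rt-CGMS group to new is-CGMS group", and the reverse for the other arm. The primary outcome is therefore complete before anyone changes device.

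The design is also described as "Open label crossover RCT with 3 arms", and the Methodology section says "Individuals will act as their own control thereby removing confounding factors in analysis". For continuous outcomes, however, the Statistical Analysis section names only independent-group tests: "ANOVA or Mann Whitney U test will be applied to compare 3 groups at a time depending upon the normality of the data". No paired or mixed model appears, and no period, sequence or carry-over term. All tests are two-sided at 0.05.

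**The concern.** A sample size for a difference in means depends on the SD as much as on the difference, and neither the SD nor the analysis is given here. A reader therefore cannot tell whether the 17 belongs to a parallel comparison at 3 months or to a within-person comparison over both periods. The two have very different power with the same patients.

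The risk lies in how the result is read. A non-significant 3-month difference between devices would be taken as coming from a trial with 80% power for 0.5%. The protocol does not show that its primary comparison has that power.

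**Working it through.** **Inputs.** From the protocol: difference 0.5 HbA1c percentage points; two-sided alpha 0.05; 17 needed and 20 recruited per CGM arm; 10% attrition. Hence 17/0.9 = 18.9, rounded up to 19, with 20 recruited; and 20 × 0.9 = 18 completers per arm. From the Review of Literature: DIAMOND, difference −0.6% (95% CI −0.8% to −0.3%), arms of 105 and 53; GOLD, crossover difference −0.43% (95% CI −0.57% to −0.29%), 142 patients with both periods.

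**1. Can the plan's 17 be reproduced?** Not from the stated inputs, because the SD is missing. It can be solved backwards. For a two-sample t test with n per arm, power comes from a noncentral t with 2n − 2 degrees of freedom and noncentrality 0.5 / (SD × √(2/n)).
- At SD 0.50 and n = 17: 0.5 / (0.50 × √(2/17)) = 2.92, power 80.7%.
- The largest SD that still gives 80% power is 0.505 at n = 17, 0.520 at n = 18 and 0.550 at n = 20.

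So 17 per arm is what an unstated SD of 0.50 would produce.

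**2. Illustration from DIAMOND.** Treat its adjusted interval as a simple two-sample one with everyone analysed.
- Standard error = (0.8 − 0.3)/2 / 1.96 = 0.1276.
- SD = 0.1276 / √(1/105 + 1/53) = 0.1276 / 0.1685 = 0.757.
- The limits are printed to one decimal. Half-widths of 0.20 and 0.30, the rounding extremes, give SDs of 0.606 and 0.908.

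| Completers per arm | SD 0.606 | SD 0.757 | SD 0.908 | Difference detectable with 80% power at SD 0.757 |
|---|---|---|---|---|
| 18 | 67% | 49% | 36% | 0.73% |
| 20 (no attrition) | 72% | 53% | 40% | 0.69% |

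Using the pooled error of a three-group ANOVA with 18, 18 and 36 completers (69 df) barely changes the middle figure: 49.8%.

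**3. Within-person reading.** From GOLD, the standard error is (0.57 − 0.29)/2 / 1.96 = 0.0714, so the SD of the within-person difference is 0.0714 × √142 = 0.851 (0.82 to 0.88 from rounding). With 2 × 18 = 36 completers, noncentrality 0.5 × √36 / 0.851 = 3.53 and 34 df, power is 93% (94% to 91% over the rounding range).

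That assumes no differential carry-over. In a two-period crossover a difference λ between the devices' carry-over shifts the expected estimate from δ to δ − λ/2. If the device with the larger effect also leaves the larger carry-over:
- λ equal to half the effect (0.25): expected estimate 0.5 − 0.125 = 0.375, power 73%.
- λ equal to the whole effect (0.50): expected estimate 0.5 − 0.25 = 0.25, power 40%.

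**The case against.** **The arithmetic is not shown to be wrong.** This stands. At SD 0.50 the 17 is correct, so the defect is an unsupported input and an unstated analysis, not a miscalculation.

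**DIAMOND is a weak proxy.** This also stands. It compared CGM with usual care over 24 weeks, at baseline HbA1c 7.5% to 9.9% against 8% to 12% here. Its interval is adjusted and coarsely rounded. A reader might infer that the trial has only about 49% power, or that 0.50 is wrong; the documents support neither. What they do support is narrower: every SD compatible with the rounded interval exceeds 0.52, and no other cited result supplies an SD near 0.50. The baseline HbA1c spreads quoted from other studies do not help either way, because turning them into an SD of change needs a correlation that no document gives.

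**The crossover supplies the power.** A reader might infer that own-control comparison makes the 80% conservative. The documents do not bear this out. The primary time point precedes the switch and no within-person analysis is specified. The switch is direct with no washout stated, whereas GOLD had 17 weeks. The Hypothesis section expects two weeks of CGM with education to improve longer-term control, and expects rt-CGM to do better. A lasting effect common to both devices would cancel, but a larger lasting effect from one device would not, and the hypothesis makes that plausible.

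**17 might be a total.** Attrition is applied in each group to reach 20 per CGM arm, which favours the per-arm reading. As a total of 17 crossover patients, 80% power would need an SD of difference of about 0.69; at 0.851 power would be about 62%.

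**Conclusion.** The point holds, as one that should be fixed. The protocol relies on 80% power for 0.5% without the SD, source or test that would support it. For the primary 3-month comparison the claim is true only if the SD is at most about 0.50 with 17 per arm, or 0.52 with 18 completers. On the DIAMOND-based illustration, power with 18 per arm is about 49% (36% to 67%), short of 80% throughout. That range reflects rounding only, not the differences between the two trials, so confidence in the size of any shortfall is moderate.

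The within-person comparison could be well powered, at about 93%, but only if differential carry-over is negligible. It cannot carry the 80% claim for an outcome measured before the switch.

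**What to change.** Rewrite the sample-size paragraph, without enrolling more patients:

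- State the SD, its source and the test, and tie the calculation to the 3-month between-group comparison of rt-CGM and is-CGM. If an SD near 0.50 can be cited, the 80% may stand.
- Otherwise make the claim conditional, for example: *With 18 evaluable patients per CGM arm, a 0.5% difference is detected with 80% power only if the SD of change is at most about 0.52. At 0.76, back-calculated from DIAMOND and illustrative only, power is about 49% and the difference detectable with 80% power is about 0.73%.*

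In the Statistical Analysis section, add a within-person rt-CGM vs is-CGM analysis of the two-period data with period and sequence terms, and label it as assuming no differential carry-over. If its power is quoted, give 93% together with the 73% and 40% carry-over cases, and do not use it alone to justify the 80%.

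The cost is one rewritten paragraph and a short addition to the analysis section. The drawback is a less favourable stated power unless an SD near 0.50 can be sourced.

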Hasaga et al conducted a trial recently to compare the efficacy of real-time and intermittently scanned continuous glucose monitoring (rtCGM and isCGM, respectively) in maintaining optimal glycemic control in T1D patients with normal hypoglycemia awareness (Gold score <4). They used rtCGM (Guardian Connect Mobile) or isCGM (FreeStyle Libre) during 4 days of physical activity (exercise phase) and in the subsequent 4 weeks at home (home phase). Primary end points were time in hypoglycemia (<3.9 mmol/L [<70 mg/dL]) and time in range (3.9–10.0 mmol/L [70–180 mg/dL]). The isCGM group wore an additional masked Enlite sensor (iPro2) for 6 days to check for bias between the different sensors used by the rtCGM and isCGM systems. In total, 60 adults with T1D (mean age 38.613 years; A1C 62.612 mmol/mol [7.861.1%]) were randomized to rtCGM ($n = 30$) or isCGM ($n = 30$). It was found that percentage of time in hypoglycemia (<3.9 mmol/L [<70 mg/dL]) was lower among rtCGM versus isCGM participants in the exercise phase (6.865.5% vs. 11.468.6%,

respectively; P50.018) and during the home phase (5.362.5% vs. 7.36 4.4%, respectively; P 5 0.035) with hypoglycemia differences being most notable during the night. Also, rtCGM participants spent more time in range (3.9–10 mmol/L [70–180 mg/dL]) than isCGM participants throughout both the exercise (78.5610.2% vs. 69.7616%, respectively; P50.0149) and home (75.669.7% vs. 67.4 6 17.8%, respectively; P 5 0.0339) phases. Final conclusion was that rtCGM was superior to isCGM in reducing hypoglycemia and improving time in range in adults with T1D with normal hypoglycemia awareness, demonstrating the value of rtCGM alarms during exercise and in daily diabetes self management.

To the best of our knowledge only one study comparing rt-CGMS vs is-CGMS is there in T1D adult patients in individuals with normal hypoglycemic awareness. With multiple limitations like no cross-over and no assessment of change in HbA1c and CGMS device being continuously worn which is not practical in our scenario.

The current thesis protocol supersedes on these limitations.

HYPOTHESIS

rt-CGMS is better than is-CGMS for short term effect on glycemic control which also will be translated into longer term glycemic control as reflected by improvement in HbA1c.

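### Arms are balanced on baseline HbA1c, but the HbA1c analysis ignores baseline and stratum and does not name the variable tested

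*Combined protocol and SAP*

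**What the plan says.** - **Randomisation (Methodology).** "Blocks of patients with HbA1c 8%-10% and 10%-12% will be distributed equally in all 3 groups". The text does not use the word stratified, but that is the natural reading. Allocation is 1:1:2, with 20, 20 and 40 patients on rt-CGMS, is-CGMS and SMBG.
- **Analysis (Statistical Analysis).** For continuous outcomes: "ANOVA or Mann Whitney U test will be applied to compare 3 groups at a time depending upon the normality of the data". No covariate, stratum, period or patient term appears, and HbA1c is not mentioned in the section.
- **Primary objective.** "Reduction in HbA1c (at the end of 3 months"), comparing rtCGM with isCGM.
- **Sample size (Materials and Methods, item 2).** 17 patients, 80% power and alpha 0.05 to "detect 0.5% change in HbA1c between both groups".
- **Review of Literature, closing remarks.** The earlier rt-CGM versus is-CGM trial is criticised for "no cross-over and no assessment of change in HbA1c".
- **Outcome variables to be studied.** "HbA1c in each of the 3 groups at end of 3 and 6 months respectively", with no mention of change.
- **Methodology, crossover.** "Individuals will act as their own control thereby removing confounding factors in analysis". No paired or crossover test follows.

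**The concern.** By balancing the arms within two HbA1c bands, the plan treats baseline HbA1c as prognostic. Balancing makes the between-arm difference less variable than under simple randomisation. An analysis that leaves the strata out still counts the between-stratum spread as error, so its standard error is too large, its interval too wide and its true test size below 5%.

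The objective, the sample-size sentence and the criticism of the earlier trial lean towards change from baseline, while the outcome list reads as attained values. The statistics section does not settle it. Change removes the baseline contribution fully only when the regression slope of follow-up on baseline is 1.

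The device comparison rests on 20 patients per arm, so avoidable imprecision is costly. The point concerns the between-arm comparison at month 3, which is the stated primary objective. In a within-patient crossover analysis the stratum would cancel, but none is named.

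**Working it through.** **1. The plan's own figure.** No SD is given, so 17 cannot be reproduced. Read as 17 per group, two-sided, it implies SD = 0.5 × √(17/2) / (1.960 + 0.842) = 0.520. Attrition: 17/0.9 = 18.9, so 19; 20 are recruited. Ten per cent loss from 20 leaves 18 per device arm, used below.

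**2. An illustrative residual SD.** The Review of Literature describes a trial of CGM against usual care (105 v 53 patients) in which "the adjusted treatment-group difference in mean change in HbA1c level from baseline was" −0.6%, with 95% CI −0.8% to −0.3%.
- SE = 0.5 / (2 × 1.96) = 0.1276
- SD = 0.1276 / √(1/105 + 1/53) = 0.1276 / 0.1685 = 0.757
- If rounding makes the true CI width 0.4 to 0.6, the SD is 0.606 to 0.908.

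**3. Model (assumed).** Month-3 HbA1c = slope × baseline + arm effect + residual. Baseline is uniform on 8–12% (SD 4/√12 = 1.155), with nine completers per stratum in each device arm. Slope = correlation × SD(follow-up) / SD(baseline). With residual SD 0.757 and correlation 0.5, 0.6 and 0.7, follow-up SD is 0.87, 0.95 and 1.06, and slope 0.38, 0.49 and 0.64.

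**4. Why the unadjusted test is conservative: change, slope 0.38.** The coefficient of baseline in change is 0.38 − 1 = −0.62, squared 0.386. Baseline variance is 2²/12 = 0.333 within strata and 1 between them (stratum means 9 and 11).
- Variance that governs the arm difference: 0.386 × 0.333 + 0.757² = 0.702
- Variance the unadjusted test estimates: 0.702 + 0.386 × 18/17 = 1.111
- True SE over estimated SE: √(0.702/1.111) = 0.795
- 95% CI half-width: 2.032 × √(1.111 × 2/18) = 0.71

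**5. Simulation, rt-CGM v is-CGM, true difference 0.5%, 20,000 runs per cell.** Entries are for correlation 0.5 / 0.6 / 0.7.

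| Residual SD 0.757 | Change | Month-3 value | ANCOVA |
|---|---|---|---|
| Power, % | 23.6 / 29.5 / 38.2 | 37.5 / 30.5 / 22.6 | 47.8 / 47.0 / 47.4 |
| Type I error, % | 1.6 / 1.9 / 3.0 | 2.8 / 2.1 / 1.4 | 4.8 / 5.0 / 5.1 |
| CI half-width | 0.71 / 0.65 / 0.58 | 0.59 / 0.64 / 0.72 | 0.52 throughout |

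| Equal SDs, 1.155 | Change | Month-3 value | ANCOVA |
|---|---|---|---|
| Power, % | 21.2 / 27.4 / 36.4 | 21.4 / 20.1 / 18.8 | 29.2 / 34.2 / 41.6 |
| Type I error, % | 3.0 / 3.4 / 3.8 | 3.0 / 2.2 / 1.4 | 5.0 / 5.1 / 5.2 |

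**6. Sensitivity.**
- Less spread baseline (SD 0.94, strata 11 and 7 per arm, residual SD 0.757): change 34.3 / 39.5 / 46.3%, month-3 value 37.4 / 30.6 / 23.1%, ANCOVA 47.4 / 47.1 / 47.6%.
- Residual SD 0.606, uniform baseline: change 22.5–39.0%, month-3 value 37.3–54.9%, ANCOVA 65.2–65.9%.
- Residual SD 0.908, uniform baseline: change 22.4–32.9%, month-3 value 15.0–25.5%, ANCOVA 34.6–35.0%.
- Slope 1 (correlation 0.84, uniform baseline, residual SD 0.757): change 49.0%, ANCOVA 47.7%, both with type I error 5.0%. There is no gain.
- Three-group test, as the plan words it, over the two settings in step 5: ANOVA type I error is 1.1–3.5% on change and 0.9–2.6% on the month-3 value. Mann-Whitney for rt v is gives 1.5–3.7% and 1.0–2.8%.

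**7. Can adjustment alone reach 80%?** With 18 v 18, difference 0.5, noncentral t on 32 df, the residual SD must be 0.519 or less.

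**The case against.** - **Change is the fair reading, and it already uses baseline.** Largely right. The benchmark is then ANCOVA against change. With equal SDs the gain is 8, 7 and 5 points at correlations 0.5, 0.6 and 0.7, about 3 points (54% v 51%) at 0.8, and nil at 0.8 with residual SD 0.757. The 24-point gain needs a uniform baseline, correlation 0.5 and a follow-up SD that shrinks from 1.15 to 0.87; the documents establish none of these. Change still carries no stratum term, and ANCOVA is never materially worse.
- **The SD is borrowed.** It comes from a rounded interval in a trial with lower baseline HbA1c (7.5–9.9%), 24 weeks of follow-up and a usual-care control. The power levels are therefore illustrative. The direction of the result does not rest on that SD.
- **The power figures are for a two-arm test the plan never names.** True. The planned test takes three groups at once, so these are not the power of the plan as written. The three-group ANOVA is conservative as well (step 6), and rt-CGM against is-CGM is the stated primary comparison.
- **The missing crossover analysis is the larger gap.** It is a separate question and does not remove this one while the primary objective is set at month 3.
- **The statistics paragraph is generic and names no outcome.** Fair: leaving the variable unnamed would by itself be only a missing detail.

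**Conclusion.** The concern holds. Baseline HbA1c is used to balance the arms and then left out of the only tests named for continuous outcomes, and the HbA1c variable tested is not fixed. The consequence is lost precision and a conservative test, with no bias and no excess of false positives.

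Under the two uniform-baseline settings, type I error at nominal 5% is 1.6–3.8% for change and 1.4–3.0% for the month-3 value, against 4.8–5.2% for ANCOVA. At residual SD 0.76 and correlation 0.5–0.7, the power gain over change is about 1 to 24 points across the two baseline shapes; it is nil at slope 1. All of this rests on an assumed SD, correlation and baseline distribution. Adjustment should be made because it costs almost nothing, but it should not be expected to rescue the stated 80% power.

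**What to change.** In Statistical Analysis, name month-3 HbA1c as the tested variable for the month-3 comparison. Analyse it by ANCOVA with arm, continuous baseline HbA1c and randomisation stratum (8–10%, 10–12%), and report the adjusted rt-CGM minus is-CGM difference with its 95% CI. State whether SMBG patients enter the model; the 32 df above assume device arms only. Treat fructosamine the same way with its own baseline, and keep the unadjusted tests as sensitivity analyses.

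State in advance whether this ANCOVA or a crossover model with sequence, period and treatment is primary. That is a separate design decision, because the switch is direct and carry-over is possible.

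Cost of the adjustment and the named variable: wording only. Baseline HbA1c is needed for eligibility and allocation. Baseline fructosamine is implied by the repeat assay after two weeks and is stated at crossover. No extra visits, samples or patients are needed.
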